STUDY SYNOPSIS

Study title	MULTICENTER, NON-INTERVENTIONAL STUDY, DESCRIBING PATIENTS WITH INHERITED RETINAL DISEASE (IRD) IN FRANCE
Short title	EPI-GenRet
Sponsor	Strasbourg University Hospitals
Coordinating/Principal Investigator	Pr [name]
Collaborative partner	Novartis Pharma SAS
HUS n°	8173
ID RCB n°	2021-A01786-35
NCT	NCT05122442
Study rationale	
Genetic diagnostic testing becomes increasingly important for enhancing our understanding of the disease notably the genetics and providing the best care to the patients ("Recommendations on Clinical Assessment of Patients with Inherited Retinal Degenerations - 2016," 2016), and several initiatives seek to gather more data in order to better understand and treat those diseases.
 
Within this context, Novartis and SENSGENE/Strasbourg University Hospitals (HUS) want to set up, through a research collaboration, a non-interventional study in France to better understand the epidemiology of IRDs, particularly the distribution of pathogenic variants in patients. This study aims to serve as a starter study to implement an IRD national registry led by SENSGENE/Strasbourg University Hospitals (HUS). The data collected might also be used to populate global European registries (cf ERN-EYE initiatives). The primary objective has been defined in a sufficient broad way to address this perspective of registries.
 
As IRDs can present from birth to late middle age, this study will include both children and adult patients regardless of age, sex, and the type of IRD.

Primary Objective	The primary objective of this study is to describe the type of IRD of patients clinically diagnosed and who attended a consultation at one of participating centers from SENSGENE network over the inclusion period.
Secondary Objectives	
The secondary objectives are stated for patients with IRD who attended a consultation at one of the participating centers from SENSGENE network over the inclusion period.
 
 • To describe the genetic diagnosis 
 ○ To describe the genetic testing characteristics ○ To describe the distribution of genes and pathogenic variants (class 4 and class 5) associated with IRDs ○ To describe the distribution of variant of uncertain significance (VUS - class 3 variants) in IRD-associated genes ○ To describe the proportion of unsolved patients ○ To describe the type of pathogenic variants in each IRD-associated gene identified

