Inclusion and non-inclusion criteria	
Only the patients who meet all the following inclusion criteria can be included in this study:
 
 • All patients, whatever age or gender, clinically diagnosed with IRD or with high suspicion for IRDs based on clinical examination and functional tests (such as fundus exam and ERG), regardless of genetic testing • Patients who attended a consultation at one of the participating centers from SENSGENE network over the inclusion period starting from sites initiation • Patients who had been prescribed a genetic test for IRD prior to or at the date of inclusion. • 
Patients who present at least one of the following non-inclusion criteria cannot be included in this study:
 
 • Patients/Parents/Legally authorized representatives (LAR) opposed to the collection and processing of their medical data/the medical data of their children/the medical data of the person for whom they are LAR; • Patients who are suffering from any other retinal disorder or optic neuropathy that may clinically or genetically overlap with IRD or non-genetic (phenocopy); • Patients/parents/Legally authorized representatives (LAR) refusing genetic testing; • Patients lacking decision-making capacity: Mental incapacity, unwillingness, or language barriers precluding adequate understanding or cooperation.
Conduct of the study	
French reference and competence centers for rare eye diseases are gathered within the SENSGENE network. The Filière de santé maladies rares (FSMR) SENSGENE fulfills national missions around rare sensory diseases with the aim of improving the care of patients, coordinating and encouraging research and developing training and information. Seven French reference and competence centers from the SENSGENE network will be contacted to participate in the study.
 
 • Five coordinating or constitutive reference centers for rare eye diseases: HU-Necker-Enfants Malades-APHP (Paris), CHNO XV-XX (Paris), CHI Créteil, HU Strasbourg, CHU Montpellier. • Two competence centers for rare eye diseases: CHU Nantes and CHU Lille
Required sample size	
This study will set up a registry that will include all eligible patients with IRD who attended a consultation at one of the participating centers from SENSGENE network.

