	
For the Cross-sectional registry no sample size calculation is required as this registry will record patient fulfilling the sets of criteria defined and will allow to have an estimation of the target population at the national level.
 
Given the capacity of sites to screen patients over one year (around 3000 patients), the inclusion of patients into the study will be limited to the first 1000 patients in order to favor the data collection quality by limiting the sites workload. This will encourage the inclusion of the patients exhaustively, especially for high volume sites for which this registry represents a deep work. However, it should be reminded that this study is a starter study that is planned to be extended to a larger national registry.
 
The precision can be estimated for a sample size of 1000 patients while considering 5% loss (patients not evaluable for the primary objective or not meeting all selection criteria).
 
The following table presents the precision and the corresponding 2-sided 95% confidence interval (CI) to describe the distribution of IRD type (proportions varying from 10% to 50% for each modality) and a sample size of 1000 patients.
 
Table. Precision and corresponding 2-sided 95% CI given the proportion of a modality varying from 10% to 50% and a sample size of 1000 patients (5% of non-evaluable patients)
 
  
 	Proportion	
 
 10%	20%	30%	40%	50%	
   
 n	Precision	Precision	Precision	Precision	Precision	
 
 Précision (%)	1.9	2.5	2.9	3.1	3.2	
 
 95% CI	8.1; 11.9	17.5; 22.5	27.1; 32.9	36.9; 43.1	46.8; 53.2	
  
 
The precision (e) is calculated based on the normal approximation using the following formula:
 $e = \sqrt{\frac{1,96^2 * (p - p^2)}{n}}$ 
where p is the proportion of a given modality and n is the number of patients.
		Proportion					10%	20%	30%	40%	50%	n	Precision	Precision	Precision	Precision	Precision	Précision (%)	1.9	2.5	2.9	3.1	3.2	95% CI	8.1; 11.9	17.5; 22.5	27.1; 32.9	36.9; 43.1	46.8; 53.2
	Proportion																													
	10%	20%	30%	40%	50%																									
n	Precision	Precision	Precision	Precision	Precision																									

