Précision (%)	1.9	2.5	2.9	3.1	3.2																									
95% CI	8.1; 11.9	17.5; 22.5	27.1; 32.9	36.9; 43.1	46.8; 53.2																									

Statistical method
	
A descriptive analysis will be conducted on all study endpoints for which data has been collected both for the overall study population and per subgroups of interest where relevant (e.g. patients' clinical characteristics, classification (class 4 and 5), nature of the mutation, the values of visual acuity (VA) and visual field (VF), date of genetic testing, clinical phenotype, type of genetic analysis performed and unsolved patients) as long as that the sizes of the sub-groups are relevant for statistical estimations. The subgroups' modalities and associated endpoints will be detailed in the Statistical Analysis Plan.
 
The following statistics will be provided for quantitative variables: number and proportion of patients with non-missing and missing
																													

	
values per variable, mean, standard deviation (StD), median, first quartile (Q1), third quartile (Q3), minimum and maximum value, the mode (especially for discrete quantitative variables with limited variability).
 
For qualitative variables, the number and proportion of each variable modality will be provided together with the number of missing values. Proportion will be computed based on the population with non-missing data.
 
Exploratory comparison between study subgroups might be considered. Statistical tests will be based on the type and distribution of the variables. All comparison tests will be two-tailed with a standard type 1 error threshold of 5% (significance level).
 
The enrollment of patients in the study will be limited to a maximum of 1000 patients, registered over a variable period of time limited to 12 months.
 
This study design therefore presents bias related to the heterogeneous duration of patients' inclusion which depends on the activity size of each participating physician.
 
In order to take into account the biases associated with this study design and be able to extrapolate results at the national level, an adjustment is planned for descriptive analyses over the registry using a weight applied at center level.

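### A weight on seven named centres, as described, gives no basis for national-level estimates; inference should be limited to eligible patients at the participating centres

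*Combined protocol and SAP*

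**What the plan says.** All references are to the synopsis in the combined protocol and SAP.

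- **Statistical method.** Inclusion stops at 1000 patients or 12 months, and the section acknowledges bias from unequal inclusion duration, which it links to each physician's activity. To handle the design's biases and make it possible to "extrapolate results at the national level, an adjustment is planned for descriptive analyses over the registry using a weight applied at center level". No formula, reference population or totals follow.
- **Required sample size.** The registry "will allow to have an estimation of the target population at the national level". This sentence does not mention a weight. The section also gives the precision table, and it says, as Study design does, that "this study is a starter study that is planned to be extended to a larger national registry".
- **Conduct of the study.** "Seven French reference and competence centers from the SENSGENE network will be contacted to participate in the study". The section then lists them in two groups: "Five coordinating or constitutive reference centers for rare eye diseases", and "Two competence centers for rare eye diseases: CHU Nantes and CHU Lille". No random or stratified selection is described.
- **Inclusion criteria.** Patients must consult at a participating centre, and the criteria admit only "Patients who had been prescribed a genetic test for IRD prior to or at the date of inclusion".
- **Primary Objective.** It concerns patients "who attended a consultation at one of participating centers from SENSGENE network over the inclusion period".

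**The concern.** The primary endpoint is a distribution: the proportion of patients by type of IRD. What that distribution describes depends entirely on the population it stands for. Two sections speak of the national level, while the objective and the sampling frame stop at the participating centres.

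The only bias named is that some centres contribute for longer than others. That is an imbalance among participating centres, and a centre weight can correct it. Patients who consult elsewhere had no chance of inclusion, so they can be represented only through outside information or an explicit assumption that they resemble those included. The text gives neither. If the plan is followed as written, the main result could be reported as a French national figure with an interval that reflects sampling error only. Data from these centres alone could not show how far off it is.

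**Working it through.** **1. The plan's own precision.** Inputs from Required sample size: 1000 patients, 5% not evaluable (n = 950), z = 1.96. Formula: e = 1.96 × √(p(1 − p)/n).

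| p | 10% | 20% | 30% | 40% | 50% |
|---|---|---|---|---|---|
| Computed, n = 950 (points) | 1.91 | 2.54 | 2.91 | 3.12 | 3.18 |
| Plan (points) | 1.9 | 2.5 | 2.9 | 3.1 | 3.2 |

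The table reproduces, so there is no arithmetic error. It is the precision of a simple unweighted proportion.

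**2. How far the documents' figures reach.** The only volume given is a screening capacity of about 3000 patients a year, for all sites together. The average expansion is 3000/1000 = 3.0. That takes the sample to the yearly caseload of these sites and no further.

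**3. Error left after perfect weighting within the participating centres.** Let c be the share of eligible French patients seen at these centres, and d the difference in a type's share between patients elsewhere and patients at these centres. Then national share = c × p_in + (1 − c) × p_out, and the error is (1 − c) × d. The documents give neither c nor d; the values below are assumptions.

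| d (points) | c = 30% | c = 50% | c = 70% |
|---|---|---|---|
| 0 | 0 | 0 | 0 |
| 2 | 1.4 | 1.0 | 0.6 |
| 5 | 3.5 | 2.5 | 1.5 |
| 10 | 7.0 | 5.0 | 3.0 |

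For a 20% type with the stated half-width of 2.5 points, the error exceeds the half-width when c is below 1 − 2.5/5 = 50% at d = 5, or below 1 − 2.5/10 = 75% at d = 10. At d = 2 it never does.

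With no linking assumption at all, a type at 20% inside the centres lies nationally between c × 20% and c × 20% + (1 − c). That is 16% to 36% at c = 80%, and 8% to 68% at c = 40%.

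**4. Does weighting cost precision?** An assumed illustration: seven centres of equal volume, with windows of 2, 3, 4, 4, 4, 5 and 6 months (mean 4 = 12 × 1000/3000, taking capacity as eligible flow) and shares of 20, 25, 30, 30, 35, 40 and 45%.

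- Weighted share: the simple mean, 225/7 = 32.14%. Unweighted share: 34.46%.
- Kish design effect = mean(window) × mean(1/window) = 4 × 0.2786 = 1.114. Half-width 1.96 × √(0.3214 × 0.6786 × 1.114/950) = 3.13 points.
- Variance stratified by centre, Σ p_i(1 − p_i)/(49 n_i) with n_i = 950 × window/28: half-width 3.02.
- Unweighted formula: 2.97 at 32.14%, 3.02 at 34.46%.

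If the target is the yearly caseload and inclusion is treated as random, the finite-population factor √(1 − 950/3000) = 0.83 would reduce the weighted half-widths further. A loss of precision is therefore not established.

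**5. Physician or centre.** Statistical method ties inclusion duration to the physician's activity but applies the weight by centre. Study design and Provisional schedule imply a window that runs from site initiation to a study-wide stop. If all physicians at a centre share that window, a centre weight is adequate for unequal duration; if they do not, it is not. The sections do not settle which applies.

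**The case against.** The strongest reply is that the text is silent on the weight, not wrong about it. No formula is given, and a centre-level weight could in principle carry external totals, for example by centre type, since both reference and competence centres take part. This stands in part. A reader might infer that the weight can only ever represent the participating centres, and the documents do not show that. They show that nothing described would take it further. Statistical method does refer to a Statistical Analysis Plan, but for the subgroups and their endpoints, not for the weight.

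A second reply is that every figure for the national error is assumed. That is correct. A reader might infer from the larger entries that the national figure will be seriously wrong. At a 2-point difference the error stays inside every stated half-width, and with equal case mix it is zero.

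A third reply is that the objective already names participating centres, the study is presented as a starter, and restriction to patients prescribed a genetic test can be read as part of the target. This is fair, and the test criterion is not counted here as a separate gap. But it supports narrowing the national wording rather than keeping it.

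Finally, an unweighted precision table with its formula shown is ordinary at the planning stage. That also stands; only a label is needed.

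**Conclusion.** The point holds in limited form. As described, the centre weight can correct unequal inclusion duration among the participating centres, but it gives no basis for a national figure. The national wording goes beyond the plan's own primary objective and its description of a starter study.

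The size of any national error is unknown. The range of 0.6 to 7 points rests on assumed coverage of 30–70% and assumed differences of 2 to 10 points, and equal case mix would remove the error entirely. A reader might also infer that the precision table is wrong or that weighting will widen the intervals materially. The table is arithmetically right, and a stratified calculation in one assumed example shows almost no loss. The physician-versus-centre wording is a matter for reconciliation, not a demonstrated flaw.

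This should be fixed, because it concerns the population behind the primary result and is inexpensive to correct before reporting.

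**What to change.** 1. In Required sample size and Statistical method, limit inference to patients who meet the inclusion criteria and attend the participating centres, and leave national estimates to the extended registry. National wording could stay only if the external totals, their source and the assumption linking these centres to the rest are prespecified.
2. Keep the centre weight for unequal inclusion duration, and define it as each centre's eligible flow over a common reference period divided by its patients included. The common period is essential: inclusion is meant to be consecutive and exhaustive, so over a centre's own window the ratio is close to 1.
3. Label the precision table as unweighted. Report weighted and unweighted proportions, with a variance that reflects the weights and the centres.
4. Reconcile Statistical method with Study design and Provisional schedule on whether inclusion windows are set by physician or by centre.

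Cost: the 1000-patient cap stays and no extra patients are needed. The conclusion becomes narrower. Eligible flow must be recorded by centre, since only an aggregate of about 3000 is given, and this adds some site work. The alternative of keeping a national claim would require external data.
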